#### **Secondary Objectives**

To evaluate the effects of zinc supplementation QD on fever, dyspnea, diarrhea, and clinical parameters of disease, and time to worsening clinical status.

### **Study Endpoints**

#### **Primary Endpoints**

- Number of days since admissions to clinical recovery
- Change in IL-6 levels from baseline to Week 2.
- Percentage of patients with disease progression by Week 2 based on WHO 9-point ordinal scale

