Finally, considering the new knowledge that this project will generate about the role of zinc in immune responses and viral expansion, we expect that our results will help researchers and physicians to design novel strategies to boost specific immune cell subpopulations against SARS-CoV2 infection. Thus, this knowledge could be used long-term for designing medicines against SARS-CoV-2 and other viral infections.

- **HYPOTHESIS AND DESCRIPTION OF THE PROJECT OBJECTIVES**

We hypothesize that low zinc nutritional status has an impact on COVID-19 progression and that adjustment of this status might constitute an early therapeutic intervention point by balancing immune responses and acting as an antiviral agent. This hypothesis is supported by the following observations:

- Zinc nutritional status impacts on innate and adaptive immunity and influences inflammatory markers(4).

- Zinc has a direct antiviral activity against specific viruses like rhinovirus, HCV, SARS-CoV(16).

- Zinc supplementation has benefits on the recurrence and persistence of acute and chronic viral infections like common cold, or HCV, HBV (2,6) and reconstitutes the production of interferon-alpha from elderly persons(16).

-Our recent data in a cohort of 249 COVID-19 patients show that COVID-19 patients with lower plasma zinc content have worse prognosis, increased time of hospitalization and mortality and that Zn and IL-6 levels are negatively correlated (13). However, the cause-effect association between nutritional zinc status and COVID-19 inflammatory response remains unproven,

-Our recent data in cell culture studies show that low zinc levels correlate with higher SARS-CoV-2 expansion(13).

The main aim of the project is to explore the therapeutic benefit of Zn supplementation for COVID-19 patients and to determine the cellular and molecular basis of the effect of Zn levels on SARS CoV-2 infections. To address these questions, we propose the following aims:

- **To study the impact of zinc supplementation on COVID-19 progression. There are two specific objectives:**

- **To carry out the clinical trial with COVID-19 patients (Subproject 1):**

We will run a randomized clinical trial with 60 COVID-19 patients admitted at Hospital del Mar with a control and a zinc supplementation group.

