**Inclusion Criteria**

To be eligible to participate in this study, all of the following criteria must apply:

- Subject is  $\geq 18$  years of age.

- Male or female.
- Subject with diagnosis of COVID-19 based on + RNA or IgM test or compatible clinical presentation.
- Ability to take oral zinc supplementation.
- Subject or surrogate decision maker is capable of understanding and willing to sign the informed consent form.

**Exclusion Criteria** and withdrawals are detailed in the document sent to the Ethics Committee.

Subjects are not permitted to enroll in the study if any of the following criteria apply:

- Female subjects who are pregnant
- Female subjects who are breast-feeding.
- Difficulty or inability to take oral medication.
- Subject is enrolled in another randomized clinical trial in the last 3 months.
- Life expectancy less than 72 hours at hospital admission.
- Conditions that in the opinion of the investigator may interfere with the subject's ability to comply with this protocol (e.g drug abuse, psychiatric disorders).

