### **Task 1.1.1 Visits and sample collection**

1.- Visit 1. Screening. Randomization. Baseline. Phase / Visit 0 or 1 ( Day 1 or up to 1 day  
Prior to Baseline/Randomization; In Person)

Visit performed at admission (+1). Written informed consent obtained. Medical history.  
Vital signs assignment. Clinical labs (CBC, CMP, CRP, ferritin, D-dimer,IL-6, zinc)

2.-Visit 2 / Week 1 (Day 7  $\pm$  2 days)

A complete record of AEs and concomitant therapies will be taken into account. 3.-

Visit 3 / Week 2 (Day 14  $\pm$  2 days), End of Treatment

A complete vital sign assessment (sitting blood pressure, heart rate, respiratory rate, O2  
sat, and oral temperature) review and record AEs and concomitant therapies, clinical  
labs (stated above) and PBMCs. Collect blood samples for future studies.

4.-Visit 4 / End of Study (Day 28  $\pm$  4 days)

Clinical labs (stated above) and PBMCs. Collect blood samples for future studies.

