### **Task 1.1.2 Assessment of Efficacy**

#### **Outcomes measured.**

- Clinical recovery
  - Defined: Sat O2 (0.21) >94% or to baseline Sat O2 in case of chronic respiratory

- Temperature <37C
  - Heart Rate <90 bpm & Systolic blood pressure >100
  - Oral tolerance
  - Baseline consciousness
- 
- Assessment of Covid-19 Disease Severity as per the WHO 9-point ordinal scale  
Ordinal scale, 9 points
  - IL-6 levels

**EO:** We expect to prove the effectiveness of zinc supplementation to reduce COVID-19 severity and mortality

**D1:** Guideline for zinc-based nutritional supplementation to treat COVID-19 patients admitted in hospitals

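### Days to recovery run from admission and entry does not require a patient to be unrecovered, so some outcomes may be fixed before zinc can act, diluting this endpoint

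*Combined protocol and SAP*

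**What the plan says.** **Endpoint.** Under Primary Endpoints, the first item is "Number of days since admissions to clinical recovery". The clock starts at hospital admission, not at randomisation or first dose. Determination of sample Size bases the 60 subjects on this endpoint.

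**Recovery definition.** Task 1.1.2 (Outcomes measured) lists room-air saturation above 94% or the patient's chronic baseline, temperature below 37C, "Heart Rate <90 bpm & Systolic blood pressure >100", oral tolerance and baseline consciousness. It gives no minimum duration. It does not say that the first time all criteria are met is the event, or how to score a patient who meets them at baseline.

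**Eligibility.** The only disease-related inclusion criterion is "Subject with diagnosis of COVID-19 based on + RNA or IgM test or compatible clinical presentation". The others are adulthood, ability to take oral zinc, and consent. None of the printed exclusions concerns a patient who is already recovered. The text adds that exclusions and withdrawals "are detailed in the document sent to the Ethics Committee", a document not available here.

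**Timing.** Task 1.1.1 says of Visit 1: "Visit performed at admission (+1). Written informed consent obtained". Study phases allows screening up to one day before baseline and starts treatment on Day 1. The first dose can thus fall about one day after admission, or about two if the windows add.

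**The concern.** Set side by side, the definition and the criteria leave a gap. An inpatient with a positive test, 96% saturation on room air and normal vital signs is eligible and already satisfies the recovery definition at baseline. Oral tolerance is close to guaranteed, because patients who cannot take oral medication are excluded. A second route comes from the clock: a patient who first meets the criteria after admission but before the first dose also counts as a recovery.

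In either case zinc cannot have influenced the result. If such patients are scored at or near zero days in both arms, they pull the two means together and add spread. The plan has little power to spare on this endpoint, so even a modest share would matter.

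**Working it through.** **Inputs from the plan** (Determination of sample Size): 60 randomised 1:1, 10% dropout, alpha 0.05, difference 3 days, SD 4 days, 80% power. Evaluable per arm: n = 30 × 0.9 = 27. Sidedness is not stated; two-sided is used.

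**Step 1: the plan's own figure.** Noncentrality = 3 / (4 × √(2/27)) = 2.756.
- Normal approximation: Φ(2.756 − 1.960) = 78.7%.
- t-test with 52 degrees of freedom: 77.2%.

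The stated 80% is reproduced to within about 1 to 3 points. The t-test value is the reference below.

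**Step 2: assumptions the documents do not supply.** Let f be the share of patients whose recovery precedes any possible effect. No value is given, so 5%, 10% and 20% are tried. Such patients are scored at zero days, which is also an assumption because the plan has no scoring rule. The 3-day difference and SD of 4 are taken to apply to the remaining, unrecovered patients.

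**Step 3: dilution.** Mean difference between arms = 3 × (1 − f).

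**Step 4: spread, treated two ways.**
- (a) SD held at 4.
- (b) SD widened by the zeros. Arm variance = (1 − f) × 16 + f(1 − f) × μ², with μ = 8 days in control and 8 − 3 = 5 days on zinc, averaged over arms. The 8 days is the recovery time of the normal-zinc group in the observational cohort (Preliminary Results), borrowed here as an assumption. Example at f = 10%: control 14.4 + 0.09 × 64 = 20.16; zinc 14.4 + 0.09 × 25 = 16.65; average 18.405; SD 4.29.

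**Step 5: power, two-sided t-test, 27 per arm.**

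| Share f | Difference (days) | (a) SD 4 | (b) SD | (b) power |
|---|---|---|---|---|
| 0 | 3.00 | 77.2% | 4.00 | 77.2% |
| 5% | 2.85 | 72.9% | 4.16 | 69.5% |
| 10% | 2.70 | 68.2% | 4.29 | 62.2% |
| 20% | 2.40 | 58.1% | 4.46 | 49.2% |

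**Step 6: the alternative reading.** If the 3 days and SD of 4 already describe everyone the criteria admit, the dilution is inside the planning figures and the loss against plan is zero.

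**Step 7: the clock alone.** Suppose half the patients start on the day of admission and half a day later. The offset has variance 0.25, the SD becomes √(16 + 0.25) = 4.03, and power is 76.5%, under 1 point lower. The offset is balanced by randomisation and does not shift the mean difference.

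**Step 8: false positives.** Simulating 10% and 20% zero-day patients with no treatment effect, 27 per arm, gives a t-test type I error of about 5% (4.8% to 5.1%).

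**The case against.** The strongest reply is that the planned difference and SD are given for the arms as randomised, not for an unrecovered subset. Read that way, nothing is lost against plan. This stands as a possible reading; the plan does not say which population its figures describe.

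The share may also be small. The project description says: "We will run a randomized clinical trial with 60 COVID-19 patients admitted at Hospital del Mar". All the listed criteria must hold together, so an inpatient failing any one of them is unrecovered. The observational recovery times of 8 and 25 days do not suggest that recovery on the day of entry is common. Some such patients may also leave the per-protocol set, although anyone who returns at Week 2 is kept. All of this limits the likely size. None of it supplies a rule for these patients, and the unseen ethics document may or may not contain one.

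Two stronger readings are tempting and do not hold.
- **Chance imbalance as a spurious effect.** Under the 8-day assumption, three extra zero-day patients in one arm would move its mean by 3 × 8 / 27 = 0.9 day, and a reader might infer a misleading treatment effect, the more so in an open-label trial. But this is ordinary sampling variation, already covered by alpha, as Step 8 shows. Open-label treatment cannot change who had recovered before randomisation.
- **Bias from the admission clock.** The offset is short and balanced between arms in expectation.

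**Conclusion.** The gap is real on the printed text: the clock starts before treatment, no listed criterion requires a patient to be unrecovered, and no rule covers those who already are. The consequence is dilution and lost power on days to recovery. The IL-6 and progression endpoints are not affected in the same way.

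The size is unknown. The power ranges of 69-73%, 62-68% and 49-58% at shares of 5%, 10% and 20% are a sensitivity analysis, not a forecast. They rest on an assumed share, on zero-day scoring, on applying the planning figures to unrecovered patients only and, at the lower ends, on assumed means of 8 and 5 days. A reader might infer that the trial really has about 49% power; the documents do not support that, because they give no share. The point deserves correction because the fix is cheap and the sizing has little margin.

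**What to change.** 1. Define the endpoint as days from randomisation (Day 1) to first meeting all the recovery criteria in Task 1.1.2.
2. Pre-specify that the days-to-recovery analysis includes only patients with at least one objective component (saturation, temperature, heart rate or systolic pressure) unmet at baseline, recorded before the allocation is known. Because the rule uses only pre-randomisation data, it introduces no bias.
3. Do not apply this restriction to the IL-6 and progression endpoints, for which mild patients remain informative; keep all randomised patients there.
4. State which population the 3-day difference and SD of 4 describe.

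**Cost.** Wording only, since vital signs are already taken at Visit 1. The recovery analysis becomes slightly smaller. With 27 × (1 − f) per arm, difference 3 and SD 4, t-test power is about 75%, 73% and 67% at f = 5%, 10% and 20%. That is better than either column in Step 5 but does not restore 77%.

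Making the rule a trial-wide inclusion criterion would keep the full number for this endpoint, at the price of slower recruitment and the loss of mild patients from the other two primary endpoints. It is optional, and should first be checked against the exclusion document sent to the Ethics Committee.

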### **3. PRELIMINARY RESULTS:**

Our preliminary results are shown in the work entitled “**Low zinc levels at clinical admission associates with poor outcomes in COVID-19**” (13) which is the result of a tight collaboration between the laboratory of [name] (Hospital del Mar) and those of [name] and [name] (both at DCEXS, UPF).

This work aimed to focus clinical attention on serum zinc content (SZC) in COVID-19 patients. Our analysis showed a robust correlation between low SZC with COVID-19

severity and mortality. The cause is likely to be a combination of immune system imbalance and a direct benefit of viral replication.

A summary of the results obtained:

- In our retrospective observational study with 249 COVID-19 patients, **23% of the patients had at admission SZC lower than 50µg/dl**, the cutoff associated with ZD and development of clinical signs.
- Our study showed that **low SZC correlates with higher IL-6 and C-reactive protein at admission**, higher peak IL-6 during the episode.
- We detected in the low SZC group that subjects needed higher time to recover (25 days) versus the control group (8 days). In the same direction, the **mortality in low SZC patients was higher (21%) than in the control group (5%)** with normal zinc concentration.
- **SARS-CoV2** Infections in cell culture demonstrated that **low zinc levels favors SARS-CoV2 viral expansion** in the infected cells.

These results highlighted the urgent need to start clinical trials supplementing with zinc low SZC patients at admission to reestablish zinc homeostasis in order to study the cause-effect association between zinc nutritional status and COVID-19 progression. We expect with this new project that zinc supplementation in low SZC COVID-19 patients will

balance what has been called the cytokine storm caused by SARS-CoV-2 and as a consequence will reduce COVID-19 severity and mortality.

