### **1) Clinical trial objectives**

#### **Primary objective**

To evaluate the effectiveness of oral zinc supplementation (83.91 mg zinc acetate) Zinc+NM QD (80mg Zn2+) QD as compared to placebo as compared to control group without zinc supplementation to reduce IL-6 increase in the course of SARS-CoV-2 infection, to decrease days to clinical recovery and to decrease the percentage of people with COVID-19 who have disease progression by Week 2, defined as inpatients, worsening of  $\geq 1$  level on the WHO 9-point ordinal scale

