#### **Secondary Endpoints**

- Change in Covid-19 signs/symptoms: dyspnea, diarrhea, temperature, neutrophil count... at Week 2

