**Study phases (4 weeks):**

- Screening + Randomization + Baseline Visit (Visit 1, same day as or up to 1 day before Baseline Visit)
- Treatment (Day 1 to Day 14) Starting on Day 1 (Baseline/Randomization), Randomized subjects will receive 80mg zinc for 2 weeks. Day 7 for clinical state. Day 14 follow up visit.
- Follow up phase : Day 28 for clinical state.

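### The primary IL-6 endpoint compares admission with Day 14 only, so it is likely to miss, in most patients, the transient in-episode rise that the primary objective aims to reduce

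*Combined protocol and SAP*

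**What the plan says.** The combined protocol and SAP names IL-6 first among the effects in the Primary objective: zinc is "to reduce IL-6 increase in the course of SARS-CoV-2 infection". Under Primary Endpoints this becomes "Change in IL-6 levels from baseline to Week 2".

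Task 1.1.1 (Visits and sample collection) sets the sampling. Visit 1, at admission, includes "Clinical labs (CBC, CMP, CRP, ferritin, D-dimer,IL-6, zinc". The same panel is repeated at Visit 3 (Day 14 ± 2) and Visit 4 (Day 28 ± 4). For Visit 2 (Day 7 ± 2) the only entry is "A complete record of AEs and concomitant therapies will be taken into account". The Study phases section describes that visit as "Day 7 for clinical state". The Clinical Laboratory Assessments paragraph of the Statistical analysis section agrees: it summarises laboratory values at baseline and Visits 3 and 4, not Visit 2.

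The Preliminary Results section gives the background. In the sponsor's cohort of 249 patients, 23% had low serum zinc at admission. Low zinc went with higher IL-6 at admission and with "higher peak IL-6 during the episode". On recovery, the low-zinc "subjects needed higher time to recover (25 days) versus the control group (8 days". The Inclusion Criteria do not require low zinc.

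**The concern.** The objective is about a rise during the illness, and part of the rationale rests on the peak. The endpoint is the difference between two values, one at admission and one about two weeks later, with nothing measured in between. A patient whose IL-6 rose after admission and had settled by Day 14 would be recorded as flat or falling, just like a patient in whom it never rose.

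At stake is how one of the three primary endpoints can be read. If zinc blunted a short-lived rise, the Week 2 change could show little or no difference between arms. The Limitation paragraph says that a finding of no benefit would mean that low zinc is a consequence of inflammation. A null IL-6 result from this schedule could not carry that inference for the in-episode rise. The gap cannot be repaired once sampling is over.

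**Working it through.** **The plan's own figure.** The documents give no power or variance figure for IL-6. The nearest is the sample size for days to recovery: 60 subjects, difference 3 days, SD 4 days, alpha 0.05, 10% dropout, 80% power. With 60 × 0.9 / 2 = 27 evaluable per arm, the two-sided normal approximation gives Φ(3 / (4√(2/27)) − 1.96) = Φ(0.796) = 78.7%, close to the stated 80%. It bears on this point only as the source of the SD of 4 used below.

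**Inputs.** 23% low zinc, hence 77% other; recovery times 25 and 8 days (all from Preliminary Results); SD 4 days (Determination of sample Size); IL-6 at Day 14 ± 2 and none at Day 7 ± 2 (Task 1.1.1).

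**Assumptions.** The 8-day figure applies to all of the other 77%. The trial enrols the cohort's mix. Recovery is counted from admission. Deaths and any treatment effect are ignored. The documents do not say whether 8 and 25 days are means or medians and give no distribution, so several shapes are tried.

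**Formula.** Share recovered by day d = 0.77 × F₈(d) + 0.23 × F₂₅(d).

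**Day 14.**
- Normal, SD 4: 0.77 × Φ(1.5) + 0.23 × Φ(−2.75) = 0.77 × 0.933 + 0.23 × 0.003 = 72%.
- Exponential, 8 and 25 as means: 0.77 × (1 − e^(−14/8)) + 0.23 × (1 − e^(−14/25)) = 0.77 × 0.826 + 0.23 × 0.429 = 73%.
- Exponential, 8 and 25 as medians: 0.77 × (1 − 0.5^(14/8)) + 0.23 × (1 − 0.5^(14/25)) = 0.77 × 0.703 + 0.23 × 0.322 = 62%.

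**Day 7.**
- Normal: 0.77 × Φ(−0.25) + 0.23 × 0.000 = 0.77 × 0.401 = 31%.
- Exponential means: 0.77 × 0.583 + 0.23 × 0.244 = 51%.
- Exponential medians: 0.77 × 0.455 + 0.23 × 0.176 = 39%.

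The table adds the edges of the Day 14 ± 2 window and, as a further check, a log-normal with medians 8 and 25 and coefficient of variation 0.5. The last column is the low-zinc share of those still unrecovered at Day 14; for the normal shape, 0.23 × 0.997 / 0.281 = 82%.

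| Shape | Recovered by Day 7 | Day 12 | Day 14 | Day 16 | Low zinc among unrecovered, Day 14 |
|---|---|---|---|---|---|
| Normal, SD 4 | 31% | 65% | 72% | 76% | 82% |
| Exponential, means | 51% | 69% | 73% | 77% | 50% |
| Exponential, medians | 39% | 56% | 62% | 66% | 41% |
| Log-normal | 30% | 63% | 70% | 75% | 69% |

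Within the low-zinc group alone, the share still unrecovered at Day 14 runs from 57% (exponential means, 1 − 0.429) to 99.7% (normal, 1 − 0.003).

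Under every shape, and anywhere in the visit window, more than half of the patients have recovered when the post-baseline IL-6 sample is taken. At Day 7 it is half or fewer, allowing for rounding.

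**The case against.** The Week 2 endpoint has a reasonable defence. Day 14 is the end of treatment. The Zinc and inflammation section names sustained IL-6 as the driver of lung damage, and a Week 2 value can detect persistence. The cohort linked low zinc to IL-6 at admission as well as to the peak. No section gives an IL-6 time course after admission, and clinical recovery in Task 1.1.2 is defined by saturation, temperature, heart rate, blood pressure, oral tolerance and consciousness, not by IL-6. Differences in admission IL-6 are balanced by randomisation in expectation. The sample size is not built on IL-6, and the two clinical primary endpoints are untouched.

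Much of this stands, and it limits the point in four ways.

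- A reader might infer that the rise is never observed, or that the endpoint cannot show an effect. The documents do not support that. About 27–38% of patients would be unrecovered at Day 14, and 41–82% of those would be low-zinc patients, the group closest to the hypothesis. A sustained rise could be seen in them.
- A reader might take the recovery shares as the share of IL-6 information lost. They measure clinical recovery. The step to IL-6 is an assumption.
- A reader might expect a Day 7 sample to capture the peak. It would not do so reliably: 31–51% would have recovered by then, and one sample with a ± 2 day window only approximates a maximum.
- A reader might extend the argument to the Week 2 signs and symptoms. No floor can be calculated for them from the documents, and Day 7 is already a clinical-state visit, so that extension is not made.

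What the defence does not answer is that the objective speaks of an increase during the infection, while no IL-6 sample is planned between admission and about Day 14.

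**Conclusion.** The mismatch between objective and endpoint is real. The Primary objective, the Primary Endpoints, the visit schedule and the laboratory analysis paragraph, read together, leave the in-episode course of IL-6 unmeasured. With some 62–73% recovered by Day 14 (56–77% across the visit window and all four shapes), the schedule is likely to miss a transient rise in most patients. This rests on the cohort's recovery times and zinc mix carrying over to the trial, on the assumed shapes, and on IL-6 settling with clinical recovery. It does not show that the endpoint is uninformative: it remains a usable measure of IL-6 at the end of treatment. The improvement is cheap and worth making before sampling starts.

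**What to change.** Add IL-6 to Visit 2 (Day 7 ± 2) in Task 1.1.1 and include that visit in the laboratory summaries. Define the primary IL-6 endpoint as post-baseline IL-6 adjusted for admission IL-6, choosing in advance either the Day 7 value or the higher of Day 7 and Day 14. If the higher value is chosen, state how patients with only one of the two samples are handled. Keep the Week 2 value, also adjusted for admission IL-6, as a supporting analysis.

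If a Day 7 sample cannot be added, reword the Primary objective as IL-6 at Week 2 adjusted for admission IL-6. State also that a null result is not evidence that zinc has no effect on the in-episode rise. That costs only a change of wording.

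The first option costs one blood tube and one assay for each of about 60 patients at an existing visit, plus a short return for those discharged before Day 7. Its remaining limit is that a single Day 7 value approximates the peak and does not capture it.

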### **Statistical analysis**

**Randomization: Subjects** will be randomized in a 1:1 ratio to:

- 83.91 mg zinc acetate (Zinc+NM) QD + standard of care for 2 weeks
- Standard of care for 2 weeks

**Determination of sample Size:** Sample size calculations are aimed at comparisons of days to clinical recovery between zinc supplementation and standard of care alone. Assuming alpha = 0.05 and a 10% dropout rate, randomization of 60 subjects will

provide 80% power to detect a difference in time to recovery between arms of 3 days assuming a SD of 4 days. This sample size will also provide at least 80% power to detect a change in percentage of people with clinical progression of 5% based on an estimated

clinical progression rate of 20% in the standard of care arm.

**Analysis Populations:** The analysis population for efficacy will be per protocol which includes all randomized subjects who complete 2 weeks of therapy and/or return for Week 2 visit. All safety analyses will include all randomized subjects who are

administrated at least 1 packet of the investigational product.

**Baseline Characteristics:** Demographics and Baseline characteristics will be summarized descriptively by group and overall using per protocol population. The following Baseline

characteristics will be summarized: sex, race, age, comorbidities, ethnicity

**Clinical Laboratory Assessments:** Blood chemistry, hematology parameters will be summarized at Baseline as well as visit 3 and 4. Laboratory values at Baseline and subsequent changes in laboratory values will be summarized descriptively overall and

by therapy group.

**Vital signs:** Vital sign measurements will be summarized at Baseline, Week 2 and Week 4. In addition, changes from Baseline to Week 2 or 4 will be summarized. For each summary the number, mean, median, standard deviation, minimum, and maximum

values will be presented overall and by therapy group.

**Safety Analyses:** All safety analyses will be based on the Safety Population, comprising all subjects who are randomized to the therapy group and subsequently receive at least one packet of investigational product. Safety assessments will be analyzed by frequency of events/abnormalities for categorical values or summarized using descriptive statistics

(mean, standard deviation, median, range, and number of observations).

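### Three primary endpoints share one alpha of 0.05 with no decision rule; if any one significant result counted as success, the family-wise error would be up to about 14%

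*Combined protocol and SAP*

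**What the plan says.** The Primary Endpoints section has three separate bullets: "Number of days since admissions to clinical recovery", "Change in IL-6 levels from baseline to Week 2" and "Percentage of patients with disease progression by Week 2 based on WHO 9-point ordinal scale". None is marked as leading. The Primary objective names the same three effects in one sentence, IL-6 first, joined by the word *and*. The Study Design section describes the trial as evaluating disease severity and IL-6, and does not mention recovery.

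Under Determination of sample Size, the Statistical analysis section states: "Sample size calculations are aimed at comparisons of days to clinical recovery between zinc supplementation and standard of care alone". Alpha appears only there: "Assuming alpha = 0.05 and a 10% dropout rate, randomization of 60 subjects will" give 80% power for a 3-day difference with an SD of 4 days. The paragraph adds that the same number also gives at least 80% power for progression. IL-6 has no power statement.

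The rest of the Statistical analysis section covers randomization, analysis populations, descriptive summaries, safety and missing data. It names no hypothesis test for any primary endpoint and does not say how the three results combine into a conclusion.

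**The concern.** With three primary endpoints and no rule, the reader cannot tell what result would make the trial positive. The choice could be made after the results are known, and one significant result out of three, for example IL-6 alone, could then be reported as effectiveness. The error rate attached to such a claim would not be the 5% that the sample-size paragraph suggests.

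This matters because the trial is not presented as purely exploratory. Task 1.1.2 expects to prove effectiveness and names a guideline for zinc supplementation in admitted patients (D1) as the deliverable.

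**Working it through.** **Inputs from the plan.** Three primary endpoints (Primary Endpoints); alpha 0.05, 60 randomised, 10% dropout, difference 3 days, SD 4 days (Determination of sample Size); 1:1 allocation (Randomization).

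**Assumptions.** Two-sided tests, because sidedness is not stated. Each endpoint is tested at the full 0.05. Test statistics are treated as jointly normal in the correlated cases.

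**1. The plan's own power figure.** Evaluable patients: 60 × 0.90 = 54, or 27 per arm. Standardised difference: 3/4 = 0.75. Normal approximation: 0.75 × √(27/2) = 2.756; 2.756 − 1.960 = 0.796; Φ(0.796) = 78.7%. The exact t-test gives 77.2%. With all 30 per arm the figures are 82.8% and 81.5%. The stated 80% is therefore approximately reproduced for recovery at a single two-sided 0.05, with no allowance for other primary endpoints.

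**2. Family-wise error if any one success counts.** All three null hypotheses true, two-sided 0.05 each:

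- Independent tests: 1 − 0.95³ = 1 − 0.8574 = 14.3%.
- Equal pairwise correlation, by simulation (2,000,000 draws):

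| Correlation | Any of three significant | Any of three significant in favour of zinc |
|---|---|---|
| 0 | 14.3% | 7.3% |
| 0.3 | 13.6% | 6.8% |
| 0.5 | 12.5% | 6.2% |
| 0.7 | 10.9% | 5.5% |

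For jointly normal two-sided tests the independence value is the maximum (Šidák inequality). With no assumption about dependence, the bound is 3 × 0.05 = 15%.

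**3. False findings in favour of zinc.** Under independence: 1 − 0.975³ = 1 − 0.9269 = 7.3%, against 2.5% for one endpoint. The ratio is 7.3/2.5 = 2.9, much the same as 14.3/5 = 2.9.

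**4. Error if all three must succeed.** This cannot exceed the size of a single test, so it is at most 5%.

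**5. Cost to recovery power of two possible rules** (27 per arm, exact t-test).

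- Recovery tested first at 0.05: 77.2%, unchanged.
- Bonferroni at 0.05/3 = 0.0167: 61.2% (64.1% by the normal approximation). Restoring 80% would take 2 × (2.394 + 0.842)² / 0.75² = 37.2, so 38 evaluable per arm; 38/0.90 = 42.2, so 43 per arm or 86 randomised.

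**The case against.** **The plan does not say that any one success is enough.** This is the strongest objection, and it stands. A reader might infer that the plan as written tests each endpoint at 0.05, lets any one carry the trial, and so has a 14% error rate. The documents do not support that: alpha appears only in the sample-size paragraph, no test is named, and no success rule is given. The *and* in the Primary objective would fit an all-must-succeed rule, under which the error is at most 5%. But that sentence lists aims and does not set a decision rule, so it settles the matter in neither direction.

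**The 14% overstates the harm described.** A false claim of benefit counts only errors in favour of zinc: 7.3% under independence, about half the two-sided figure. This stands, although the almost threefold inflation relative to one endpoint remains.

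**The endpoints are probably correlated, and the tests are unnamed.** Both points stand. The Background reports IL-6 as associated with COVID-19 progression, so about 11% to 14% is more realistic than a single figure. The test for progression also matters: with 27 per arm and a 20% rate in both arms, Fisher's exact test has an actual size of 1.9% (family-wise 1 − 0.95² × 0.981 = 11.5% if independent), and an uncorrected chi-square 5.7% (14.9%).

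**Recovery sets the sample size, so it is the primary endpoint in practice.** This does not remove the gap. The plan never ranks recovery above the others, and the same paragraph claims power for progression as well.

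**Conclusion.** The point holds in conditional form. What is established is an omission: three primary endpoints, one alpha, and no rule for combining them. If any one significant result may count as a positive trial, which the plan leaves open, the family-wise error would be up to about 14% (14.3% if independent, about 11% to 14% at correlations of 0.7 to 0.3). The chance of a false finding in favour of zinc would be about 7.3% instead of 2.5% under independence. These figures rest on two-sided 0.05 for each endpoint, all three nulls true, and approximately normal test statistics.

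The stated 80% power for progression is a separate problem and adds no weight here. The sponsor should fix the omission, since the results are meant to support a guideline.

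**What to change.** Before any analysis of outcome data, state one decision rule, with sidedness, in Primary Endpoints and Statistical analysis. Align the Primary objective and Study Design with it; Study Design does not mention recovery at present.

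Recommended rule: test days to clinical recovery first at two-sided 0.05, because it sets the sample size. Then test IL-6 change and progression in a pre-specified fixed order, each at 0.05 and only if the preceding test is significant. Otherwise report estimates with confidence intervals. The order of the last two is the sponsor's choice; nothing in the documents fixes it.

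This holds the family-wise error at 5%, needs no extra patients, and keeps recovery power at about 77%. The cost is rewording four sections and one real concession: a significant IL-6 or progression result alone would no longer make the trial positive, although both are now stated as primary aims.

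There are two alternatives. Bonferroni keeps all three on an equal footing, but recovery power falls to about 61%, or about 86 patients are needed. An all-must-succeed rule also needs only wording, but its power cannot exceed that of its weakest endpoint; for progression at 20% versus 15% that is about 7% with 27 to 30 per arm.
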